10.3 Device Incidents

A listing of device incidents will be provided for the Safety Population.

10.4 Device Experience

The Device Experience questionnaire will be completed by parents/caregivers at the Day 12 visit. Data will be listed for the Safety Population.

10.5 Prior and Concomitant Medications

Medication use from 7 days prior to enrollment to EOS will be coded to generic terms, including 2nd-level Anatomical-Therapeutic-Chemical (ATC) drug class, using the World Health Organization Drug Dictionary (WHO-DD), version 01Mar2018B3 Enhanced. Aside from parameters collected on the eCRF, listings will include date and time of study treatment dosing, WHO-DD drug class and preferred drug name, and Study Day. Frequencies and percentages of

Confidential Page 19 of 35

subjects reporting or receiving each medication will be summarized by WHO-DD drug class and preferred name within drug class.

Medications that were stopped prior to study treatment dosing will be considered "prior" medications, medications that were stopped earlier than 7 days before enrollment will be ignored, and all other medications will be considered "concomitant." Medications recorded with insufficient exposure dates to determine whether or not they were concomitant will be considered concomitant.

Prior medications will be listed and summarized separately from concomitant medications. Listings and summaries for prior medications will be based on all subjects randomized. Listings and summaries for concomitant medications will be based on the Safety Population.

11. SAFETY PARAMETERS

Safety parameters will be listed and summarized for the Safety Population unless otherwise noted.

11.1 **AEs**

AEs reported from time of informed consent through EOS will be coded according to MedDRA® version 21.0. Each reported AE will be mapped to a PT and SOC. Aside from parameters collected on the eCRF, listings will include MedDRA PT and SOC, Study Day, whether or not the AE is ongoing, and AE duration. For AEs that are ongoing, AE end date will be imputed with subject-level EOS date for the duration calculation.

TEAEs will be AEs that began or worsened in severity during or after first dose of study treatment and no later than 2 calendar days after last dose of study treatment. AEs with insufficient date or time information to determine whether or not they were treatment-emergent will be considered treatment-emergent. AEs that began or worsened in severity from 2 calendar days after last dose through EOS will be defined as non-treatment-emergent (non-TEAEs). AEs that began or worsened in severity after informed consent but before the first dose will be counted as pre-treatment AEs.

All TEAEs will be listed. In addition, separate listings will be done for:

- Treatment-emergent SAEs (TESAEs)
- TEAEs that resulted in study treatment interruption or dose reduction
- TEAEs that results in study treatment discontinuation (excluding deaths)
- TEAEs that resulted in death
- Pre-treatment AEs among the Screened Population
- Non-TEAEs

Listings will be done for the Safety Population.

Incidence of all TEAEs will be summarized by SOC and PTs within SOCs, sorted alphabetically by SOC and PT within SOC. In addition, separate summaries will be done for:

• TEAEs assessed as related to study treatment

Confidential Page 20 of 35

- TEAEs by severity
- TESAEs
- TESAEs assessed as related to study treatment
- Pre-treatment AEs among the Screened Population
- Non-TEAEs

In summaries by relationship to study treatment, missing relationship will be considered related. In summaries by AE severity, missing severity will be counted as severe.

An overall summary of TEAEs (collapsed over all SOCs and PTs) will show incidence of all TEAEs as well as:

- TEAEs assessed as related to study treatment
- TESAEs
- TESAEs assessed as related to study treatment
- Severe TEAEs
- Moderate TEAEs
- Mild TEAEs
- TEAEs that resulted in study treatment interruption or dose reduction
- TEAEs that results in discontinuation from the study or study treatment (excluding deaths)
- TEAEs that resulted in death

Summaries of TEAEs and TESEAs (separately) in descending order of incidence among all subjects combined will show incidence of PTs only.

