### Treatment Groups and Duration:

Twice daily treatment with 10 mg intranasal OP0201 or 0 mg intranasal placebo for a total of 20 doses, as well as standard oral antibiotic treatment for a total of 20 doses, will be initiated on Day 1. The first dose of the intranasal study treatment will be administered in the study center under supervision of the study staff.

**Statistical Methods:**Power Calculation

The power calculation is based on a 2-sided Pearson chi square test of each of the 2 endpoints in the primary efficacy endpoint family and control for Type 1 error using the step-up Hochberg procedure. The minimally important difference in proportions for both endpoints is approximately 0.25. With 70 Participants randomized per treatment group, and assuming a 12% dropout rate with dropouts counted as failures, this Phase 2a study will have 87% power to detect a treatment effect in at least 1 of the 2 endpoints assuming 40% of placebo-treated Participants will have no bulging TM at Day 4 and 30% of placebo-treated Participants will have no MEE at Day 12.

Populations for Analyses

Four populations will be considered.

Screened population is defined as all Participants whose parent/legal guardian signs the informed consent form.

Safety population is defined as all Participants who received at least 1 intranasal spray of study treatment and will be used to assess the safety and secondary efficacy endpoints.

Intent-to-treat (ITT) population is defined as all randomized Participants and will be used to assess the primary efficacy endpoint family.

Per-Protocol (PP) population is defined as the subset of the ITT population who have no protocol violations affecting the primary efficacy endpoint family and will be used to confirm results from the primary efficacy endpoint family.

Statistical Analyses

The Statistical Analysis Plan (SAP) will be developed and finalized before database lock and will describe the Participant population sets to be included in the analyses, and procedures for accounting for missing, unused, and spurious data.

Safety Analyses

Safety will be evaluated using the safety population.

Treatment-emergent adverse events (TEAEs) are defined as AEs that first occurred or worsened in severity after administration of study treatment and no later than 2 calendar days after the last dose of study treatment.

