#### **8.4.1 Time Period and Frequency for Collecting AE and SAE Information**

All SAEs will be collected from the time of signed informed consent obtained until the Study Exit.

All AEs will be collected from the time of signed informed consent obtained until the Study Exit.

Medical occurrences that begin before the start of study treatment but after obtaining signed informed consent will be recorded as pretreatment-emergent AEs in the AE section of the eCRF.

All SAEs will be recorded and reported to the Sponsor or designee within 24 hours, as indicated in [Appendix 3](#). The Investigator will submit any updated SAE data to the Sponsor within 24 hours of it being available.

Investigators are not obligated to actively seek AEs or SAEs after conclusion of the study participation. However, if the Investigator learns of any SAE, including a death, within 30 days of Study Exit, and he/she considers the event to be reasonably related to the study treatment or study participation, the Investigator must promptly notify the Sponsor.

The method of recording, evaluating, and assessing causality of AE and SAE and the procedures for completing and transmitting SAE reports are provided in [Appendix 3](#).

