#### **9.4.2 Safety Analyses**

Safety will be assessed by incidence, seriousness, severity, and relatedness to study treatment of AEs and shifts from baseline (normal, abnormal) in vital signs, physical examination, and examination of the nasopharynx and oropharynx for local effects.

The Medical Dictionary for Regulatory Activities will be used to code AEs to system organ class (SOC) and preferred term. An AE that began or worsened in severity after first dose of study treatment and no later than 2 calendar days after the last dose of study treatment will be considered a treatment-emergent adverse event (TEAE).

Treatment-emergent adverse event incidence will be tabulated by primary SOC and by preferred term within each primary SOC. Summary tables will be provided for all TEAEs, serious AEs, treatment-related TEAEs and all AEs leading to discontinuation of study treatment.

No formal testing of treatment group differences will be performed for AEs.

Shifts from baseline in vital signs, physician examination, nasopharynx and oropharynx examination results will be summarized for each visit.

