## Appendix 3      Adverse Events: Definitions and Procedures for Recording, Evaluating, Follow-up, and Reporting

### Definition of Adverse Events

Adverse Event Definition

 
• An AE is any unfavorable and unintended sign (including an abnormal laboratory finding), symptom, or disease (new or exacerbated) in a Participant.
 
• An AE that occurs after informed consent is signed and prior to exposure to study treatment is a pretreatment AE.
 
• An AE that first occurs or worsens in severity after informed consent is signed and occurs after administration of study treatment, whether or not considered related to the study treatment, is a TEAE.
 

Events Meeting the Adverse Event Definition

 
• Any safety assessments (eg, vital signs measurements), including those that worsen from baseline, considered clinically significant in the medical and scientific judgment of the Investigator (ie, not related to progression of underlying disease).
 
• Exacerbation of a chronic or intermittent pre-existing condition including either an increase in frequency and/or intensity of the condition.
 
• New conditions detected or diagnosed even though it may have been present before the start of the study.
 
• Signs, symptoms, or the clinical sequelae of a suspected drug-drug interaction.
 
• Signs, symptoms, or the clinical sequelae of a suspected overdose of either study treatment or a concomitant medication. Overdose per se will not be reported as an AE/SAE unless it is an intentional overdose taken with possible suicidal/self-harming intent. Such overdoses should be reported regardless of sequelae.
 
• “Lack of efficacy” or “failure of expected pharmacological action” per se will not be reported as an AE or SAE. Such instances will be captured in the efficacy assessments. However, the signs, symptoms, and/or clinical sequelae resulting from lack of efficacy will be reported as AE or SAE if they fulfill the definition of an AE or SAE.
 

Events NOT Meeting the Adverse Event Definition

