APPENDIX B: TABLES OF CONTENTS FOR TABLES, FIGURES, AND LISTINGS

TABLES

NUMBER	TITLE	POPULATION
Study Popula	tion	
14.1.1	Subject Disposition	all randomized
14.1.2	Eligibility	all randomized
14.1.3	Reasons for Screen Failure	Screened excluding
		randomized
14.1.4	Protocol Deviations	all randomized
14.1.5	Analysis Populations	all randomized
14.1.6	Baseline Characteristics	all randomized
14.1.7.1	Medical History	all randomized
14.1.7.2	Baseline Symptoms	all randomized
14.1.8	Pre-Treatment Adverse Events	Screened
Treatments		
14.1.9.1	Study Treatment Exposure	Safety
14.1.9.2.1	Study Treatment Compliance	Safety
14.1.9.2.2	Oral Antibiotic Compliance	Safety
14.1.10.1	Prior Medications	all randomized
14.1.10.2	Concomitant Medications	Safety
Efficacy Endp	oints	
14.2.1.1	Bulging TM	mITT
14.2.1.2	Bulging TM	Per Protocol
14.2.1.3	Bulging TM	Complete Case
14.2.1.4	Bulging TM and No Recurrence	mITT
14.2.1.5	Bulging TM by age group	mITT
14.2.1.6	Bulging TM by sex	mITT
14.2.1.7	Bulging TM by race	mITT
14.2.1.8	Bulging TM by disease laterality	mITT
14.2.1.9	Bulging TM by history of recurrent AOM	mITT
14.2.1.10	Bulging TM by daycare attendance	mITT
14.2.1.11.1	Bulging TM by study site	mITT
14.2.2.1	MEE	mITT
14.2.2.2	MEE	Per Protocol
14.2.2.3	MEE	Complete Case
14.2.2.4	MEE and No Recurrence	mITT
14.2.2.5	MEE by age group	mITT
14.2.2.6	MEE by sex	mITT
14.2.2.7	MEE by race	mITT
14.2.2.8	MEE by disease laterality	mITT
14.2.2.9	MEE by history of recurrent AOM	mITT
14.2.2.10	MEE by daycare attendance	mITT
14.2.2.11.1	MEE by study site	mITT
14.2.3.1	Tympanogram Shifts from Baseline	Tympanogram Subset
14.2.4.1	AOM-SOS Scale Score – 10-Day Mean	mITT
14.2.5.1.1	AOM Cure	mITT

Confidential Page 32 of 35

14.2.5.1.2	AOM Cure – Sensitivity Analysis	mITT
14.2.6.1	AOM-SOS Response	mITT
14.2.7.1	AOM Treatment Failure, AOM Relapse, AOM Recurrence	mITT
Safety Endp	oints	
14.3.1.1	Summary of TEAE Incidence	Safety
14.3.1.2.1	Incidence of TEAEs by System Organ Class (SOC) and Preferred Term (PT)	Safety
14.3.1.2.2	Incidence of TEAEs Related to Study Treatment by SOC and PT	Safety
14.3.1.2.3	Incidence of TEAEs by Severity, by SOC and PT	Safety
14.3.1.2.4	TEAEs by PT in Descending Order of Incidence	Safety
14.3.1.3.1	Incidence of TESAEs by SOC and PT	Safety
14.3.1.3.2	Incidence of TESAEs Related to Study Treatment by SOC and PT	Safety
14.3.1.3.3	TESAEs by PT in Descending Order of Incidence	Safety
14.3.1.4	Non-TEAEs	Safety
14.3.9.1	Vital Signs, Observed Values and Changes from Baseline	Safety

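### The SAP's treatment-emergent and non-emergent AE windows share day +2, Appendix 3 has no end limit, and SAEs after the cut-off enter no SAE table or SAE listing

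*SAP*

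**What the plan says.** **Window for treatment-emergent events.** SAP 11.1 sets the upper limit of a TEAE at "no later than 2 calendar days after last dose of study treatment". Two sentences later it says that "AEs that began or worsened in severity from 2 calendar days after last dose through EOS will be defined as non-treatment-emergent". Protocol 9.4.2 uses the same upper limit as the SAP's TEAE rule ("no later than 2 calendar days after the last dose of study treatment will be considered a treatment-emergent adverse event"), and so does the safety paragraph of the protocol synopsis ("no later than 2 calendar days after the last dose of study treatment"). Protocol Appendix 3 differs: an event that first appears or worsens after consent and "occurs after administration of study treatment, whether or not considered related to the study treatment, is a TEAE". It gives no end point.

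**Serious events.** Protocol 8.4.1 says: "All SAEs will be collected from the time of signed informed consent obtained until the Study Exit". Protocol 9.4.2 then says: "Summary tables will be provided for all TEAEs, serious AEs, treatment-related TEAEs and all AEs leading to discontinuation of study treatment". In that sentence the serious category carries no treatment-emergent limit, while the related category does. The synopsis draws the same distinction. In SAP Appendix B the SAE tables are 14.3.1.3.1 ("Incidence of TESAEs by SOC and PT"), 14.3.1.3.2 and 14.3.1.3.3, and all three cover treatment-emergent SAEs. The SAE listing (14.3.2.1) and the death listing (14.3.2.4) have the same limit. Later events go to a general non-TEAE table (14.3.1.4) and listing (16.2.7.2). SAP Section 16, which lists changes from the protocol, does not mention this restriction.

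**The concern.** Two windows meant to divide follow-up share a day, and the SAP gives no rule for choosing between them. Its default to treatment-emergent applies only when date or time information is insufficient. A third definition, in Appendix 3, would label every post-dose event as emergent.

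The serious-event outputs matter more. Safety is a primary objective, and Protocol 1.1 and 2.1 say that only one child had previously received the active ingredients intranasally. A reader who opens the SAE tables will expect every SAE from first dose to study exit, as the protocol indicates. Built as the SAP specifies, those tables stop two days after the last dose, and nothing in Section 16 warns of it.

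**Working it through.** The plan states no figure to reproduce. The check compares definitions and counts calendar days.

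**Inputs**
- Treatment: 20 doses twice daily over 10 days (SAP Section 3); the protocol says approximately 10 days. The last dose L is Day 10 as planned. Day 11 is an assumption, for a child who receives only one dose on Day 1.
- Visit 3 window: Days 12 to 14. Visit 4 window: Days 26 to 30 (SAP 8.7; Protocol Table 3).
- Follow-up after treatment: up to 20 days (SAP Section 3). Check: Day 30 − Day 10 = 20, which agrees.

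**Step 1: the overlap.** TEAE days satisfy day ≤ L + 2. Non-TEAE days satisfy day ≥ L + 2. The only shared day is L + 2, which is Day 12 for L = 10 and Day 13 for L = 11. Both lie inside the Visit 3 window. If the non-TEAE rule becomes day > L + 2, the overlap falls from one day to none.

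**Step 2: days beyond the cut-off.** For exit on day E, the number of days after the cut-off is E − (L + 2).

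| Last dose | Exit | Days after cut-off | Share of study days |
|---|---|---|---|
| Day 10 | Day 26 | 26 − 12 = 14 | 14/26 = 54% |
| Day 10 | Day 28 | 28 − 12 = 16 | 16/28 = 57% |
| Day 10 | Day 30 | 30 − 12 = 18 | 18/30 = 60% |
| Day 11 (assumed) | Day 26 | 26 − 13 = 13 | 13/26 = 50% |
| Day 11 (assumed) | Day 28 | 28 − 13 = 15 | 15/28 = 54% |
| Day 11 (assumed) | Day 30 | 30 − 13 = 17 | 17/30 = 57% |

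The range is 13 to 18 days. With the longest follow-up, 18 of the 20 post-treatment days (90%) lie beyond the cut-off. Appendix 3 would class all of these days as emergent.

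**Step 3: where a late SAE appears.** Take an SAE with onset on Day 15 after a last dose on Day 10. Appendix 3 makes it a TEAE. SAP 11.1 and Protocol 9.4.2 do not. Under SAP Appendix B it is therefore outside all three SAE tables and the SAE listing, and outside the death listing if fatal. It appears in 14.3.1.4 and 16.2.7.2 with every other late event. Nothing in the plan says that table 14.3.1.4 separates serious from non-serious events.

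**The case against.** The best defence is that the intended window is clear. The synopsis, Protocol 9.4.2 and the SAP's own TEAE rule all include day +2, and non-TEAE is by name the complement of TEAE, so a programmer would probably read *from* as *more than*. Appendix 3 governs how investigators record events, and AEs are collected to study exit whatever their label. Late SAEs also remain visible: they are reported to the sponsor within 24 hours, they have a table and a listing, and SAP 11.1 says listings carry the eCRF fields. A treatment-related SAE would also meet the study-stopping criterion in Protocol 5.4.1, so it could hardly pass unnoticed.

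Most of this stands, and it limits the point. Four stronger readings are tempting and are not supported:
- *Day +2 events will be counted twice.* They qualify for both categories, but neither document says that they enter both tables.
- *Events will cluster on day +2 because examination findings take the visit date as onset.* Neither document states such a rule. AEs are reported by the parent or caregiver (Protocol 8.4).
- *The related and severity tables also break a protocol promise.* The protocol itself limits the related summary to TEAEs and promises no severity table for the whole period.
- *Late SAEs are lost.* They are in the non-TEAE outputs.

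The defence does not answer the SAE outputs. The protocol distinguishes serious AEs from TEAEs, the SAP does not, and Section 16 is silent.

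**Conclusion.** The point holds in three parts of unequal weight. The shared day +2 is a wording error affecting one calendar day per child, and the other statements of the window show which way to resolve it. The open-ended Appendix 3 definition contradicts the synopsis, Protocol 9.4.2 and SAP 11.1; no effect on a specific table has been shown. The unrecorded narrowing of the SAE outputs is the substantive part: an SAE dated to the last 13 to 18 study days, half or more of the study period, would be in no SAE table and no SAE or death listing.

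The count assumes treatment completed on schedule, a last dose on Day 10 (or Day 11, assumed) and exit on Days 26 to 30. It does not describe children who stop early. It applies to events with usable dates, since others default to treatment-emergent. The documents give no expected SAE rate, so the number of events affected cannot be estimated. This is a modest reporting fault that does not touch the efficacy analysis. It is worth correcting before database lock.

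**What to change.** 1. In the non-TEAE sentence of SAP 11.1, replace *from* with *more than*, so that the class begins on the day after day +2.
2. Align the TEAE definition in Protocol Appendix 3 with Protocol 9.4.2.
3. Make the SAE table and the SAE and death listings cover all events from first dose to study exit. Show the treatment-emergent subset within them and display relatedness for each SAE.

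The general related-event and severity tables may stay treatment-emergent only, as the protocol itself limits related events that way. If the sponsor prefers to keep the SAE outputs restricted, Section 16 should record and justify the restriction. That would make the change visible but would still leave late SAEs without an SAE table.

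The cost is one wording correction, one aligned definition, and a small amount of programming to widen the filter on outputs already planned. No new data are needed, because SAEs are already collected to study exit.

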11.2 Vital Signs

Vital signs will be collected at each study visit. Observed values for oral temperature, respiratory rate, and pulse will be summarized at each time point. Changes from baseline will also be summarized for each post baseline time point. Listings will include changes from baseline.

11.3 Physical Examination

Physical examination will be done at each study visit. Findings for each body system, including extended data for throat and nose, will be summarized. Body system shifts from baseline to normal/abnormal status will also be summarized.

11.4 Ear Examination

Examination of each ear will be done at each study visit. Summaries, by ear and visit, will be done for: TM findings (intact, perforated,), color (gray, pink, pale yellow, white, amber, blue), translucency (translucent, semi-opaque, opaque), mobility (none, 1+, 2+, 3+, 4+), air fluid interface (yes, no), otalgia (yes, no), distinct erythema (yes, no), position of the TM (neutral, retracted, 1+ bulging, 2+ bulging, 3+ bulging), otorrhea (no, serous, purulent), and diagnosis (no effusion, OME, AOM).

Confidential Page 21 of 35

Shift tables will summarize changes from baseline in normal/abnormal status, where "abnormal" will be limited to "definitely abnormal" defined as follows:

• TM findings: perforated

• Color: pale yellow, white, amber, blue

• Translucency: semi-opaque or opaque

• Mobility: none

• Air fluid interface: yes

• Otalgia: yes

• Distinct erythema: yes

• Position of TM: retracted, 1+ bulging, 2+ bulging, 3+ bulging

• Otorrhea: serous, purulent

Diagnosis: AOM, OME

Parameters will be summarized within treatment group for (a) first or only affected ear and (b) second or non-affected ear. Since either one ear or both ears can have AOM at baseline, this approach will allow descriptive comparisons between OP0201 and placebo treatment groups on number of affected ears (ie, one or both ears) and shifts from baseline, by visit, for both affected and non-affected ears at baseline.

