### 5.1 Inclusion Criteria

Participants are eligible to be included in the study only if all the following criteria apply:

3. Male and female infants and children aged 6 to 24 months (inclusive).
4. Diagnosis of AOM - moderate to severe bulging of the TM (Key Action Statement 1A), or mild bulging of TM and recent (less than 48 hours) onset of ear pain (otalgia) (Key Action Statement 1B), or mild bulging of the TM and intense erythema of the TM (Key Action Statement 1B).
5. Score of 5 or more on the 5-question version of the AOM-SOS scale.
6. Intact TM in both ears (eg, no perforation).
7. Written informed consent by the infant/child's parent/legal guardian and their willingness to ensure that study instructions are followed, all study-related visits are attended, that treatment administration is given, and the parent/caregiver assessments are recorded according to the study protocol.
8. Parent/Legal Guardian has a smartphone or internet access to receive the electronic survey.

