4.2 Study Endpoints

4.2.1 Safety Endpoints

- Incidence, seriousness, severity, and relationship to IP of treatment-emergent adverse events (TEAEs)
- Shifts from baseline (normal, abnormal) in vital signs (temperature, respiratory rate and pulse)
- Shifts from baseline (normal, abnormal) in physical examination, including visual examination of the nasopharynx and oropharynx
- Shifts from baseline in examination of the TM (via otoscopy and endoscopy)

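### The ear-safety tables pool second AOM ears with non-AOM ears, so the stated comparison of shifts in non-affected ears is not delivered for most parameters

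*SAP*

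**What the plan says.** SAP 4.2.1 lists among the safety endpoints "Shifts from baseline in examination of the TM (via otoscopy and endoscopy"; Protocol Section 3 places the same examination under the primary objective. SAP 11.4 sets the layout: "Parameters will be summarized within treatment group for (a) first or only affected ear and (b) second or non-affected ear". Its reason begins "Since either one ear or both ears can have AOM at baseline", and it says the approach will allow descriptive comparison of the arms on the number of affected ears and on "shifts from baseline, by visit, for both affected and non-affected ears at baseline".

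Two outputs carry this in SAP Appendix B: Table 14.3.9.3.1 (observed findings) and Table 14.3.9.3.2 (shifts). On the shifts, SAP 11.4 says "Shift tables will summarize changes from baseline in normal/abnormal status", with abnormality defined parameter by parameter. Two of those definitions matter here: "Diagnosis: AOM, OME" and "Position of TM: retracted, 1+ bulging, 2+ bulging, 3+ bulging". Protocol 5.1 requires at entry "Intact TM in both ears (eg, no perforation".

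The unilateral/bilateral subgroup in SAP 8.4 applies only to the primary efficacy endpoints. Randomization (SAP 6.1) is stratified by daycare and age, not by laterality.

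**The concern.** Each child contributes one ear to each group. Group (a) is uniform: one AOM ear per child. Group (b) is not. In a bilateral child it is an ear with AOM at entry; in a unilateral child it is an ear without. No group consists only of non-affected ears, although the SAP names them as one of the two things to be compared.

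At stake is how well the tables show new pathology in ears that did not have AOM at entry. Change in an AOM ear reflects the course of the disease and the antibiotic as well as the study treatment. Change in a non-AOM ear is less entangled with these. Protocol 2.1 says only one child had previously received the active ingredients intranasally, so a readable summary of such change is worth having.

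**Working it through.** The plan states no figure on this point, so there is none to reproduce. The check asks which non-affected-ear shifts can be recovered from group (b), and how large the ambiguity is where they cannot.

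**1. Which parameters can be read**

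A shift table crosses baseline normal/abnormal status with later status. Non-affected ears are isolated only where the baseline-normal row cannot contain an AOM ear. The AOM definition in Protocol 5.1 always requires bulging.

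- *Diagnosis.* Normal means no effusion, so the baseline-normal row of (b) holds only non-AOM ears. Readable.
- *TM position.* Normal means neutral, so no AOM ear is in that row. Readable.
- *TM integrity.* Every ear is intact at entry, so all of (b) sits in one baseline row. Not readable.
- *Color, translucency, mobility, air fluid interface, otalgia, erythema, otorrhea.* The AOM definition fixes none of these: moderate to severe bulging qualifies alone, and mild bulging needs otalgia or intense erythema but not both. A second AOM ear can be normal on any one of them and share the row with non-AOM ears. Not readable.

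Even for the two readable parameters, a non-AOM ear with OME or a retracted TM at baseline falls in the abnormal row beside the second AOM ears.

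**2. Composition of group (b)**

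Inputs: n = 70 children per arm (SAP Section 5); bilateral share b, not given, assumed 20% to 70%. Second AOM ears = n × b; non-AOM ears = n × (1 − b).

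| b | Second AOM ears | Non-AOM ears |
|---|---|---|
| 20% | 14 | 56 |
| 50% | 35 | 35 |
| 70% | 49 | 21 |

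**3. Ambiguity for perforation**

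Suppose k = 7 new perforations among the 70 group (b) ears, a pooled 7/70 = 10.0%. The count is illustrative. Among m non-AOM ears the number perforated lies between max(0, k − second AOM ears) and min(k, m).

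- b = 20%: 0 to 7 of 56, or 0% to 12.5%.
- b = 50%: 0 to 7 of 35, or 0% to 20.0%.
- b = 70%: 0 to 7 of 21, or 0% to 33.3%.

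**4. Effect of a chance imbalance in laterality**

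Let p2 and pu be the abnormal rates in second AOM and non-AOM ears, equal in both arms. The pooled rate is b × p2 + (1 − b) × pu, so the arms differ by (b1 − b2) × (p2 − pu). Assume p2 = 70% and pu = 20%, a gap of 50 points.

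- Shares of 40% and 50%: pooled 40% and 45%, a difference of 5 points.
- Shares of 40% and 60%: pooled 40% and 50%, a difference of 10 points.

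The SD of the chance difference in bilateral share is √(2b(1 − b)/70), treating allocation as simple randomization.

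- b = 50%: √(0.50/70) = 0.0845; × 1.96 = ±16.6 points in share; × 0.50 = ±8.3 points in the pooled rate.
- b = 20%: √(0.32/70) = 0.0676; ±13.3 points in share; ±6.6 in the rate.
- b = 70%: √(0.42/70) = 0.0775; ±15.2 points in share; ±7.6 in the rate.

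For TM integrity at baseline the gap is zero, so there is no distortion.

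**The case against.** Much of the promise is kept. Group (a) gives an affected-ear comparison. The baseline AOM count in group (b) is the number of bilateral children, so the arms can be compared on number of affected ears and a laterality imbalance would be visible. Movement from no effusion to OME or AOM, or from neutral to bulging, can be read for non-AOM ears. Listing 16.2.9.3 lets a reader rebuild the split child by child. The table shells are in separate documents (SAP 8.2) and may already separate the ears. The comparison is descriptive, and no decision rule depends on it.

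All of this stands as a limit on the point. It does not remove it. A listing worked through by hand is not the summary the SAP describes, and the grouping is specified in the SAP text, whatever the unseen shells show.

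Three stronger readings are tempting, and the documents do not support them. A reader might infer that nothing about non-affected ears can be read; diagnosis and TM position show otherwise. A reader might call these ears healthy; the SAP's term means only that they lacked AOM, and they may have OME or be retracted. A reader might take the range of about ±17 points as the possible chance difference in abnormal rates between arms; it is the range for the bilateral share at an assumed 50%, and it carries over in full only if every second AOM ear is abnormal and every non-AOM ear normal on that parameter.

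**Conclusion.** The point holds in a limited form. The layout in SAP 11.4 does not deliver the non-affected-ear comparison for eight of the ten ear parameters, perforation being the clearest. It delivers it for diagnosis and TM position only among ears normal at baseline.

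The size depends on the bilateral share, which the documents do not give, and on the assumed perforation count and abnormal rates. Under those assumptions a pooled 10% perforation rate leaves the non-AOM rate open between 0% and 20% at 50% bilateral, and a chance laterality imbalance moves pooled rates by roughly ±7 to ±8 points. This is a minor reporting matter: no test, endpoint definition or efficacy conclusion is affected.

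**What to change.** In SAP 11.4 and Tables 14.3.9.3.1 and 14.3.9.3.2, replace the two ear groups with three, defined by the ear's own AOM status at baseline:

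- the first or only AOM ear;
- the second AOM ear (bilateral children);
- the non-AOM ear (unilateral children).

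Give each its own denominator in each arm, and check that the table shells match.

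No new data are needed, because each ear is already examined and recorded separately at every visit. The cost is one more row block in two descriptive tables, with smaller denominators: for non-AOM ears, 56, 35 or 21 per arm of 70 at assumed bilateral shares of 20%, 50% or 70%.
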